### **Ensuring strict adherence to the clinical study protocol**

The clinical study will be carefully monitored by the Sponsor monitor (or designee) to ensure adherence to the CIP. AEs and device deficiencies will be reported to Abbott/designee and will be monitored internally for safety surveillance purposes.

### **15.6 Risk to Benefit Rationale**

The XIENCE Skypoint stent diameters 4.5 and 5.0 mm were approved for commercial use in the US. The foreseeable rates of the anticipated AEs associated with the procedure and implantation of XIENCE Skypoint stent diameters 4.5 and 5.0 mm are listed in the IFU and in **Appendix III**. The clinical benefit that may be expected from treatment of coronary lesions with large diameter with the XIENCE Skypoint stent diameters 4.5 and 5.0 mm outweighs the possible risks that subjects may experience when participating in this trial.

**APPENDIX I: ABBREVIATIONS AND ACRONYMS**

Acronym or Abbreviation	Complete Phrase or Definition
%DS	percent diameter stenosis
ACC/AHA	American College of Cardiology/American Heart Association
AE	adverse event
AMI	acute myocardial infarction
ARC	Academic Research Consortium
BMI	body mass index
CABG	coronary artery bypass graft
CAD	coronary artery disease
CD	cardiac death
CEC	clinical events committee
CIP	clinical investigation plan
COPD	chronic obstructive pulmonary disease
COVID-19	coronavirus disease 2019
CK-MB	creatinine kinase myocardial-band isoenzyme
CT-FFR	computed tomography-fractional flow reserve
cTn	cardiac troponin
DAPT	dual antiplatelet therapy
DD	device deficiency
DES	drug-eluting stent
DFR	diastolic hyperemia-free ratio
DM	device malfunction
DPR	diastolic pressure ratio
ECG	electrocardiogram
eCRF	electronic case report form
EDC	electronic data capture
EECS	everolimus eluting coronary stent
EECSS	everolimus eluting coronary stent system
FAS	full analysis set
FDA	The Food and Drug Administration
FPI	first-patient-in

Acronym or Abbreviation	Complete Phrase or Definition
GCP	good clinical practice
HBR	high bleeding risk
ICF	informed consent form
IFU	instructions for use
iFR	instantaneous wave-free ratio
ID	ischemic driven
IRB	institutional review board
IVUS	intravascular ultrasound
LMCA	left main coronary artery
LPO	last-patient-out
mg	milligram
MI	myocardial infarction
mm	millimeter
NSTEMI	non-ST-Elevation MI
NQMI	non-Q wave myocardial infarction
OCT	optical coherence tomography
OUS	outside of United States
PBMA	poly (n-butyl methacrylate)
PCI	percutaneous coronary intervention
PVDF-HFP	polymer of vinylidene fluoride and hexafluoropropylene
QCA	quantitative coronary angiography
QMI	Q wave myocardial infarction
RFR	resting full-cycle ratio
RVD	reference vessel diameter
RX	rapid exchange
SAE	serious adverse event
SOC	standard of care
ST	stent thrombosis
STEMI	ST-elevation MI
TBD	to be determined
TIMI	thrombolysis in myocardial infarction

Acronym or Abbreviation	Complete Phrase or Definition
TLF	target lesion failure
TLR	target lesion revascularization
TVF	target vessel failure
TVR	target vessel revascularization
ULN	upper limits of normal (per site standard)
URL	upper reference limit (per assay IFU)
US	United States

## APPENDIX II: DEFINITIONS

### ACC/AHA Classification Scheme of Coronary Lesions: Lesion-Specific Characteristics

Type A Lesions (High Success, >85%; Low Risk)	

 
Discrete (< 10 mm length)
 
Concentric
 
Readily accessible
 
Nonangulated segment, < 45°
 
Smooth contour
 
	
 
Little or no calcification
 
Less than totally occlusive
 
Not ostial in location
 
No major branch involvement
 
Absence of thrombus
 

Type B Lesions* (Moderate Success, 60-85%; Moderate risk)	

 
Tubular (10-20 mm length)
 
Eccentric
 
Moderate tortuosity of proximal segment
 
Moderately angulated segment, > 45°, < 90°
 
Irregular contour
 
	
 
Moderate-to-heavy calcification
 
Total occlusions < 3 months old
 
Ostial in location
 
Bifurcation lesions requiring double guide wires
 
Some thrombus present
 

* Type B1 lesions: One adverse characteristic * Type B2 lesions: ≥ two adverse characteristics	
Type C Lesions (Low Success, <60%; High Risk)	

 
Diffuse (> 2 cm length)
 
Excessive tortuosity of proximal segment
 
Extremely angulated segments > 90°
 
	
 
Total occlusions > 3 months old
 
Inability to protect major side branches
 
Degenerated vein grafts with friable lesions
 

### DEATH (Per ARC Circulation 2007; 115: 2344-2351)

All deaths are considered cardiac unless an unequivocal non-cardiac cause can be established. Specifically, any unexpected death even in subjects with coexisting potentially fatal non-cardiac disease (e.g. cancer, infection) should be classified as cardiac.

#### Cardiac death:

Any death due to proximate cardiac cause (e.g. MI, low-output failure, fatal arrhythmia), unwitnessed death and death of unknown cause, all procedure related deaths including those related to concomitant treatment.

**Vascular death:**

Death due to non-coronary vascular causes such as cerebrovascular disease, pulmonary embolism, ruptured aortic aneurysm, dissecting aneurysm, or other vascular cause.

**Non-cardiovascular death:**

Any death not covered by the above definitions such as death caused by infection, malignancy, sepsis, pulmonary causes, accident, suicide or trauma.

## MYOCARDIAL INFARCTION [MI]

### 1. Periprocedure MI

#### Periprocedural MI – Modified ARC-2 Definitionxii

Periprocedural myocardial infarction occurring within 48 hours after all percutaneous coronary intervention (PCI) and coronary artery bypass grafting (CABG) procedures:

Absolute rise (from baseline to within 48 hours of procedure) in cardiac troponin of  $\geq 35\times$  the 99th percentile upper reference limits (URL) (or  $\geq 35\times$  upper limits of Normal [ULN] if URL is not available) or in the absence of cardiac troponin, rise in CK-MB to  $\geq 5\times$  the 99th percentile URL (or  $\geq 5\times$  ULN if URL is not available). Note, cardiac troponin assessments are preferentially used if available; otherwise CK-MB may be used.

In addition, 1 (or more) of the following measures of myocardial ischemia must be present post-procedure:

- New significant Q waves ( $\geq 40$  ms in duration and  $\geq 1$  mm deep in voltage in  $\geq 2$  contiguous leads) or equivalent
- Persistent flow-limiting angiographic complications in a major epicardial vessel or branch  $\geq 1.5$  mm in diameter present at the end of the PCI procedure (or during angiography performed to evaluate a post-CABG complication) as assessed at the angiographic core laboratory
- New substantial loss of viable myocardium on serial imaging

These assessments apply to patients: a) with baseline CK-MB or cardiac troponin levels  $\leq 1\times$  the 99th percentile URL (or  $\leq 1\times$  ULN if URL is not available); b) in whom the baseline biomarker is  $> 1\times$  the 99th percentile URL (or  $> 1\times$  ULN if URL is not available) and stable or falling; and c) with a single elevated baseline draw who have a chronic coronary syndrome (CCS). In the latter two groups (patients in whom the baseline is elevated and stable or falling and CCS patients with a single elevated baseline draw), the post-procedural troponin (or CK-MB) must rise above the most recent baseline by an increment of the values above (i.e. for troponin  $\geq 35\times$  the 99th percentile URL or  $\geq 35\times$  ULN if URL is not available) or in the absence of cardiac troponin, for CK-MB  $\geq 5\times$  the 99th percentile URL (or  $\geq 5\times$  ULN if URL is not available).

xii Garcia-Garcia HM, McFadden EP, Farb A, et al. Standardized End Point Definitions for Coronary Intervention Trials: The Academic Research Consortium-2 Consensus Document. *Eur Heart J*. 2018;39(23):2192-2207.

These assessments do not apply to patients: a) in whom baseline CK-MB or troponin levels are elevated and rising; and b) with a single elevated baseline level who presented with a NSTEMI or STEMI in whom it is uncertain whether the peak has been reached. In such patients periprocedural MI will only be adjudicated if the troponin (or CK-MB) biomarker increases from the prior measure by the increments thresholds specified above, and at least 2 of the 3 above criteria for myocardial ischemia are present.

Periprocedural MI per SCAI definition J Am Coll Cardiol. 2013; 62(17):1563-70):

defined as the occurrence within 48 hours after either PCI or CABG of either:

- CK-MB above 10 x URL (\*determined on a single measurement), OR
- CK-MB above 5 x URL (\*determined on a single measurement), PLUS
  - new pathological Q waves in at least 2 contiguous leads or new persistent non-rate related LBBB

In the absence of CK-MB measurements and a normal baseline cardiac troponin (cTn), peri-procedural MI can also be defined as a cTn (I or T) level measured within 48 hours of the PCI rises to  $\geq 70$  x the local laboratory URL, or  $\geq 35$  x URL with new pathologic Q-waves in  $\geq 2$  contiguous leads, or new persistent LBBB.

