## 3.3 Suspension or Early Termination of the Clinical Study

## 4.0 ENDPOINTS

### 4.1 Primary Endpoint iv

The descriptive primary endpoint is Target Lesion Failure (TLF) at 1 year. iv

- TLF is defined as the composite of cardiac death (CD), myocardial infarction (MI) related to the target vessel (TV-MI), or ischemic driven target lesion revascularization (ID-TLR).
- For the assessment of periprocedural MI, modified Academic Research Consortium (ARC) II definition will be used. Cardiac troponin (cTn) will be used for the primary cardiac biomarker for MI assessment. For the assessment of spontaneous MI, the 4th universal MI definition will be used. Both MI definitions are defined in **Appendix II**.

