#### 5.3.1 Inclusion Criteria

##### 5.3.1.1 General Inclusion Criteria

1. Subjects must be at least 18 years of age.
2. Subjects or a legally authorized representative must provide written informed consent per site requirements.
3. Subjects must have evidence of myocardial ischemia (ST-elevated MI [STEMI], Non-STEMI [NSTEMI], Unstable Angina or Stable Angina) or who have silent ischemia with evidence of ischemia, appropriate for percutaneous coronary intervention (PCI) treatment of *de novo* native coronary artery lesionsvi with DES. Subjects with stable angina or silent ischemia must have an objective sign of ischemia as suggested by one of the following:
  - Abnormal stress or imaging stress test
  - Abnormal computed tomography-fractional flow reserve (CT-FFR)
  - Stenosis by visual estimation  $\geq 70\%$
  - Abnormal pressure-derived indexes (such as fractional flow reserve [FFR], instantaneous wave-free ratio [iFR], diastolic hyperemia-free ratio [DFR], diastolic resting pressure ratio [DPR], or resting full-cycle ratio [RFR]).

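### Appendix II lets an early STEMI or NSTEMI presenter with a still-normal baseline troponin meet the periprocedural MI definition on one ischaemia criterion, so the presenting infarct can be counted in primary TLF

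*Protocol*

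**What the plan says.** Protocol Section 4.1 sets the primary endpoint: "TLF is defined as the composite of cardiac death (CD), myocardial infarction (MI) related to the target vessel (TV-MI"), with ID-TLR as the third component. On the MI part it says: "For the assessment of periprocedural MI, modified Academic Research Consortium (ARC) II definition" is used. Acute infarct patients are eligible under Section 5.3.1.1: "Subjects must have evidence of myocardial ischemia (ST-elevated MI [STEMI], Non-STEMI [NSTEMI], Unstable Angina or Stable Angina"), and the visible exclusion criteria do not remove an evolving infarct.

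The modified ARC-2 text in Appendix II has two parts.

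- **Standard test.** The biomarker part is "Absolute rise (from baseline to within 48 hours of procedure) in cardiac troponin of" at least 35x URL. The ischaemia part is "In addition, 1 (or more) of the following measures of myocardial ischemia must be present post-procedure": new Q waves, a flow-limiting angiographic complication read by the core laboratory, or new loss of viable myocardium on imaging.
- **Who gets it.** "These assessments apply to patients: a) with baseline CK-MB or cardiac troponin levels" at or below 1x URL form group (a). Group (b) has an elevated baseline that is stable or falling. Group (c) has a single elevated draw in chronic coronary syndrome.
- **Who gets the stricter test.** Two of the three ischaemia criteria are needed for subjects "in whom baseline CK-MB or troponin levels are elevated and rising", and for those "with a single elevated baseline level who presented with a NSTEMI or STEMI in whom it is uncertain whether the peak has been reached".

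Section 6.1.2 accepts one baseline troponin draw and requires any repeats to be entered. The schedule in Section 6.4.4 makes the post-procedure ECG mandatory and the pre-procedure ECG a recommendation. Appendix II assigns an infarct to the target vessel unless another vessel is clearly responsible.

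**The concern.** The two-of-three rule exists because, in an acute infarct whose biomarker has not peaked, a later rise may belong to the infarct that brought the patient in. That reasoning applies most strongly to the earliest presenter, whose troponin is still normal and plainly has not peaked. Yet both routes into the stricter test require an elevated baseline, so this subject stays in group (a).

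After an uncomplicated PCI, the presenting infarct can supply the 35x rise and, as it evolves, new Q waves. That satisfies the one-criterion test. Where no pre-procedure ECG was taken, it is also harder to show that Q waves were already present.

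At stake is the primary TLF rate. This is a single-arm descriptive study, so the rate is itself the result. An entry condition counted as an outcome would raise it by an amount that depends on how many early STEMI or NSTEMI presenters are registered.

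**Working it through.** The protocol states no figure to reproduce. The check is to apply the Appendix II allocation rule to cases on either side of 1x URL. The troponin level needed is baseline + 35, in multiples of URL, because the rise is measured from baseline.

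| STEMI case | Group under Appendix II | Level needed (x URL) | Ischaemia criteria needed |
|---|---|---|---|
| Single draw 0.5x | standard (a) | 0.5 + 35 = 35.5 | 1 |
| Single draw 0.9x | standard (a) | 0.9 + 35 = 35.9 | 1 |
| Single draw 1.0x | standard (a) | 1.0 + 35 = 36.0 | 1 |
| Single draw 1.1x | stricter (b) | 1.1 + 35 = 36.1 | 2 |
| Single draw 3x | stricter (b) | 3 + 35 = 38 | 2 |
| Two draws, 0.2x then 0.9x | standard (a) | 0.9 + 35 = 35.9 | 1 |
| Two draws, 0.9x then 1.5x | stricter (a) | 1.5 + 35 = 36.5 | 2 |

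Three things follow.

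1. Between 0.9x and 1.1x URL the biomarker hurdle barely moves (35.9x against 36.1x). The required number of ischaemia criteria doubles, and the lighter burden falls on the subject sampled earlier in the infarct.
2. A documented rise does not help while both values are normal: 0.2x to 0.9x still needs only one criterion. The gap is therefore confined to subjects whose last value before PCI is at or below 1x URL.
3. A 35x rise with new Q waves and nothing else qualifies in group (a) and fails in the stricter group.

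The path to the primary endpoint is then direct. Periprocedural MI by this definition counts as TV-MI if the target vessel is the culprit or no other vessel is clearly responsible, and TV-MI is a component of TLF.

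The addition to the TLF proportion would be a product of four shares:

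- the share of subjects presenting with STEMI or NSTEMI;
- the share of those whose last pre-PCI value is at or below 1x URL;
- the share of those reaching the 35x rise with one criterion because of the presenting infarct;
- the share of those attributed to the target vessel and with no other TLF event.

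The document gives none of the four, nor a visible subject number, so no figure is offered.

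Under the amended rule given below, the 0.5x, 0.9x and 1.0x cases move from one required criterion to two, matching the 1.1x case.

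**The case against.** The strongest reply is that Appendix II defines an infarct that occurs in the 48 hours after the procedure. A presenting STEMI occurred before it, so the CEC can set it aside. Section 10.9.1 has the CEC work from its charter as well as from the protocol's definitions. The charter is not shown, and the note under the primary endpoint, the endpoint footnote, the post-procedure biomarker bullets and the troponin footnotes to the schedule are blank or redacted. Any of these may cover the case. This stands as a limit on certainty: a reader might infer that the protocol obliges the CEC to count the entry infarct, and the documents do not support that. It does not close the gap, because the visible text measures the rise from baseline and nowhere excludes the presenting infarct. The visible passage on spontaneous MI within 48 hours concerns causes distinct from the procedure, with stent thrombosis as its example.

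Four further points are fair.

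- An arterial-sheath draw is the latest possible pre-angioplasty sample, so it makes a normal baseline less likely.
- Not every such event reaches TLF. Lesions in a second vessel may be treated, and an infarct clearly due to another vessel is not TV-MI.
- It would be wrong to infer that nothing exposes the problem. TLFsp-MI is the same composite without periprocedural MI, so comparing it with primary TLF shows how much rests on periprocedural MI. It cannot separate true procedural infarcts from the presenting infarct, and it leaves the primary rate unchanged. TLF-SCAI is no cross-check: its troponin route, used without CK-MB and from a normal baseline, accepts a rise to 70x URL with no ischaemia criterion.
- Q waves and loss of myocardium can both come from the presenting infarct even in the stricter group. One might conclude that the core-laboratory complication should be compulsory. The documents do not make its absence an error, and requiring it would drop procedural infarcts shown by the other two criteria.

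**Conclusion.** The point holds as a gap in the allocation rule. Appendix II applies the one-criterion test to any subject with a baseline at or below 1x URL, including an early STEMI or NSTEMI presenter, and its safeguard for an unreached peak misses the case it fits best. As written, the presenting infarct can be adjudicated as periprocedural MI and counted in primary TLF.

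The size is unknown. It depends on the STEMI and NSTEMI share, the share with a still-normal last draw, how often the threshold and one criterion are then met, and how often the target vessel is held responsible. The conclusion assumes that the unseen charter and redacted notes do not already handle these subjects. If they do, Appendix II still needs to agree with them.

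**What to change.** Amend Appendix II as follows and mirror it in the CEC charter.

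1. Limit group (a) to subjects with a baseline at or below 1x URL who did not present with STEMI or NSTEMI.
2. Extend the existing two-of-three rule to every STEMI or NSTEMI presenter without a documented biomarker peak before PCI, whatever the baseline value. Say explicitly where a presenter belongs whose documented peak has already returned to 1x URL or below, since neither list would otherwise name that subject.
3. State that the qualifying infarct is not itself a periprocedural MI. Appendix II treats every MI that is not periprocedural as spontaneous, so the sentence should also keep the qualifying infarct out of that category.

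The cost is wording only. No extra draws are needed, because a presenter with a single baseline draw simply falls under the two-of-three rule. The downside is small: some true procedural infarcts in early presenters that show only one criterion will not be counted. The change should be settled before further events are adjudicated, so that it is not made with knowledge of outcomes.

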Follow-up	
 
At 1, 6 months, 1, 2 and 3 years, Office visits are strongly recommended for all follow-ups. Phone visits are only allowed if otherwise the subject will be missing the visits.
 

Primary Endpoint	
Target Lesion Failure (TLF) at 1 yeariv
 
 
TLF is defined as the composite of cardiac death (CD), myocardial infarction (MI) related to the target vessel (TV-MI), or ischemic driven target lesion revascularization (ID-TLR).
 
For the assessment of periprocedural MI, modified Academic Research Consortium (ARC) II definition will be used. cTn will be used for the primary cardiac biomarker for MI assessment. For the assessment of spontaneous MI, the 4th universal MI definition will be used. Both MI definitions are defined in Appendix II.
 

Secondary Endpoint	
The descriptive secondary endpoints are defined as:
 
 
Target lesion failure (TLFsp-MI) at 1 yeariv 
 
TLFsp-MI is defined as the composite of CD, and TV-MI, including spontaneous MI and excluding periprocedural MI and, or ID-TLR
 
 
cTn will be used for the primary cardiac biomarker for MI assessment. For the assessment of spontaneous MI, the 4th universal MI definition will be used.
 
Note that the study will allow CKMB on sites (Site Number:US0879) that (1) are already participating in CIP-Rev A; (2) do not have cTn as the site's SOC.
 
 
Target Lesion Failure (TLFSCAI) at 1 yeariv 
 
TLFSCAI is defined as the composite of CD, and TV-MI, including both periprocedural MI and spontaneous MI, or ID-TLR
 
For the assessment of periprocedural MI, Society for Cardiovascular Angiography and Intervention (SCAI) definition will be used, and cTn will be used for the primary cardiac biomarker for MI assessment. For the assessment of spontaneous MI, the 4th universal MI definition will be used. Both MI definitions are defined in Appendix II
 
 
 

Other Endpoints	
Clinical Outcomes will be evaluated at each follow-up time point.
 
Composite Outcomes
 
 

 

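### The SCAI CK-MB route in Appendix II ignores baseline, so a presenting infarct with CK-MB above the threshold and stable or falling counts as a periprocedural MI in TLF-SCAI

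*Protocol*

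**What the plan says.** Appendix II gives two periprocedural MI definitions.

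- **SCAI, CK-MB route.** The event is "defined as the occurrence within 48 hours after either PCI or CABG of either" of two findings: "CK-MB above 10 x URL", or CK-MB above 5 x URL together with "new pathological Q waves in at least 2 contiguous leads or new persistent non-rate related LBBB". Both thresholds are marked as judged on a single measurement. No baseline value, rise or increment is mentioned.
- **SCAI, troponin route.** This opens with "In the absence of CK-MB measurements and a normal baseline cardiac troponin (cTn", which I read as requiring both that no CK-MB was measured and that baseline troponin was normal. Troponin must then rise to 70 x URL, or to 35 x URL with new Q waves or LBBB.
- **Modified ARC-2.** When the baseline is elevated and stable or falling, the post-procedure marker "must rise above the most recent baseline by an increment of the values above". For a rising baseline, or a STEMI/NSTEMI with one elevated draw and an uncertain peak, the text says "In such patients periprocedural MI will only be adjudicated if the troponin (or CK-MB) biomarker increases from the prior measure" by the threshold amount, and two of three ischemia criteria must also be present.

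Section 5.3.1.1 admits acute infarction: "Subjects must have evidence of myocardial ischemia (ST-elevated MI [STEMI], Non-STEMI [NSTEMI], Unstable Angina or Stable Angina". Section 4.2 includes periprocedural target-vessel MI in TLF-SCAI and names troponin as the primary marker. Appendix II attributes an infarct to the target vessel unless it clearly belongs to another. Section 10.9.1 has the CEC adjudicate by the definitions in the protocol. Appendix X adds, under the spontaneous-MI version of TLF, "Note that the study will allow CKMB on sites" that were already in Revision A and lack troponin as standard of care; one site is listed.

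**The concern.** A subject who comes to PCI because of an infarct may have a high CK-MB before the stent is placed. A rule that looks only at the post-procedure level cannot separate that infarct from one caused by the procedure. The protocol recognises the problem in its other two marker rules but not in this one.

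TLF-SCAI is a named secondary endpoint of a single-arm study, so a misclassified event enters the reported rate with no control arm to offset it. Classification would also depend on the marker. With CK-MB, an elevated and falling marker can score as an MI. With troponin alone and an elevated baseline, the SCAI text gives no way to score one at all.

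**Working it through.** The protocol gives no event rate or sample size to reproduce: the endpoints are descriptive and the numbers are blacked out. The check applies the printed rules to example records, then asks how large the effect could be.

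**Rules as printed (CK-MB in multiples of URL)**

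- SCAI: MI if post > 10, or post > 5 with new Q waves or new persistent LBBB.
- ARC-2 (CK-MB when troponin is absent): with a baseline of at most 1, post ≥ 5 plus at least one ischemia criterion. With an elevated baseline, post − baseline ≥ 5 plus at least one criterion, or at least two if rising or uncertain.
- SCAI first limb with a baseline condition: with an elevated baseline, post − baseline > 10.

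| Baseline → post | Change | SCAI as printed | ARC-2 | SCAI with baseline condition |
|---|---|---|---|---|
| 14 → 11, falling | −3 | MI | no | no |
| 15 → 12, falling | −3 | MI | no | no |
| 12 → 12, stable | 0 | MI | no | no |
| 20 → 11, falling | −9 | MI | no | no |
| 8 → 12, rising or uncertain | +4 | MI | no | no |
| 15 → 9, no new Q waves or LBBB | −6 | no | no | no |
| 0.8 → 12, normal baseline | +11.2 | MI | MI if ≥ 1 criterion | MI |

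In the first five rows the change is below 5, so ARC-2 does not score them whatever ischemia criteria are present. On the SCAI troponin route, a baseline of 100 and a post value of 90 x URL is not scored, because the baseline is not normal.

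**Path to the endpoint.** The scored MI is attributed to the target vessel by default and so counts in TLF-SCAI. The ARC-2 safeguards refer to ARC-2's own thresholds and criteria; nothing visible carries them into the SCAI text.

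**Size.** Added TLF-SCAI ≈ s × m × q, where s is the share presenting with STEMI/NSTEMI, m the share of these with a post-procedure CK-MB, and q the share of those above 10 x URL because of the presenting infarct. None of the three is in the protocol. Assume s = 20–40% and q = 30–60%:

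- m = 2%: 0.20 × 0.02 × 0.30 = 0.12 points, to 0.40 × 0.02 × 0.60 = 0.48 points.
- m = 10%: 0.20 × 0.10 × 0.30 = 0.6 points, to 0.40 × 0.10 × 0.60 = 2.4 points.
- m = 30%: 0.20 × 0.30 × 0.30 = 1.8 points, to 0.40 × 0.30 × 0.60 = 7.2 points.

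With s = 10–30%, q = 20–50% and 5% of subjects already having a TLF-SCAI event, m = 2% gives about 0.04 (0.10 × 0.02 × 0.20 × 0.95) to 0.28 points (0.30 × 0.02 × 0.50 × 0.95). The product s × m × q also treats every case as target-vessel related and as an additional event, so for given inputs it is an upper figure.

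**The case against.** The strongest reply concerns reach. Section 4.2 and Appendix X both make troponin the primary marker for TLF-SCAI, section 6.1.2 mandates a baseline troponin, and the schedule in section 6.4.4 lists only troponin. The one visible CK-MB allowance covers a single legacy site and is printed under an endpoint that excludes periprocedural MI. This stands, with one qualification: the SCAI troponin route applies only when CK-MB was not measured, which on its face gives CK-MB precedence wherever it is drawn. The two places conflict, and the visible text does not settle which governs. A reader might infer that every site drawing CK-MB routinely is affected; that follows only if Appendix II prevails.

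Second, text that may limit CK-MB is not visible: the post-procedure biomarker bullets in section 6.3.2, footnotes iv and viii, and schedule notes 3 and 4. The CEC charter is not shown, and the SCAI definition is a condensed version of a cited consensus paper. All fair. The point is about the definition as printed, which is the one the CEC is told to apply.

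Third, a reader might infer that any STEMI or NSTEMI with a raised baseline CK-MB is scored. That is too broad: 15 → 9 x URL without new Q waves or LBBB is not. Nor is a large rise a clear false positive. A STEMI going from 8 to 25 x URL has risen by 17 x URL and would exceed a 10 x increment; the difficulty there is an uncertain peak.

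Finally, TLF-SCAI is descriptive and secondary, and the CEC reviews each MI. This limits the consequence, but CEC review does not cure a definition the committee must follow.

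**Conclusion.** The point holds for the printed definition. The SCAI CK-MB route scores a presenting infarct as a periprocedural MI when the post-procedure CK-MB exceeds the threshold, even if the marker is stable or falling. The SCAI troponin route and ARC-2 do not.

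The size cannot be established from the protocol. At 2% CK-MB use among MI presenters it is about 0.1 to 0.5 percentage points under the first set of assumptions, and more if CK-MB is drawn more often. A reader might take the 7.2-point figure as the likely inflation. It needs CK-MB in 30% of MI presenters, for which a protocol that mandates troponin and lists one CK-MB site offers no basis.

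The primary endpoint uses ARC-2 and is unaffected. The correction is worth making because it is cheap and removes a dependence of TLF-SCAI on the marker a site happens to use.

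**What to change.** In the SCAI definition in Appendix II, and in the CEC charter:

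1. Apply the CK-MB thresholds as absolute values only when baseline CK-MB is at most 1 x URL.
2. When baseline is elevated and stable or falling, require a rise above the most recent baseline of more than 10 x URL, or of more than 5 x URL plus new Q waves or new persistent LBBB.
3. When baseline is rising, its peak is uncertain, or it is missing in a STEMI/NSTEMI subject, do not score on a single CK-MB value alone. State what SCAI-specific evidence the CEC needs. ARC-2's two-of-three requirement should not be imported, because the SCAI rule does not contain those three criteria.
4. Collect a pre-procedure CK-MB wherever CK-MB is the marker used.
5. Reconcile the CK-MB precedence implied in Appendix II with troponin as primary marker in section 4.2 and Appendix X, and say whether the legacy-site allowance extends to TLF-SCAI.

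The cost is one paragraph in two documents and one extra baseline sample at the CK-MB site. That sample cannot be recovered for subjects already treated, who would fall under item 3 if they presented with STEMI/NSTEMI and have no baseline CK-MB. TLF-SCAI will be slightly lower. No treatment changes.
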